6.3 Treatment Plan

6.3.1 Induction therapy

Eligible subjects will receive induction chemotherapy with idarubicin (12 mg/m^2 intravenously for 3 days) and cytarabine (100 mg/m^2 intravenously for 7 days) starting Day 1 and ending Day 7 as described in Figure 1. Patients 80 years or older may receive 2 and 5 days of idarubicin and cytarabine respectively starting Day 1 and ending Day 5 (optional, at physician discretion). HLA-mismatched DLI will be administered Day 9

Chemo with Adoptive Haplo DLI

(DLI will occur on Day 7 for 5+2 regimen), approximately 24-48 hours following completion of chemotherapy at a dose of 1×10^8 CD3+ cells; however, due to logistics of planning infusions with staffing, donor availability, weekends/holidays, etc., it may be necessary to postpone cell infusion up to 96 hours, which will be allowed without being considered a protocol violation.

Subjects who experience no remission or partial remission will receive a second course of the identical induction chemotherapy (IND2). IND2 should include 7+3+DLI as per IND1, but if cells are not available as per 6.2.3, chemotherapy alone can be given without being considered a protocol violation.

Given the time constraints presented by the need to start induction chemotherapy as soon as possible, in some cases, it may not be logistically possible to administer cells with induction (e.g., obtaining insurance approval for clinical trial/DLI may take a while, and approval may not be back in time for a patient to receive cells). In these cases, patients would just receive standard induction chemotherapy and cells would be administered after CON1 in addition to CON2 (see below). Timing of correlative laboratory studies will be adjusted to match cell infusion. Guo et al. have reported improved outcomes with high cell doses (1×10^8 CD3+ cells/kg) administered after consolidation, even in patients who receive standard induction chemotherapy without cells.¹

¹Guo M, Hu KX, Liu GX, Yu CL, Qiao JH, Sun QY, Qiao JX, Dong Z, Sun WJ, Sun XD, Zuo HL, Man QH, Liu ZQ, Liu TQ, Zhao HX, Huang YJ, Wei L, Liu B, Wang J, Shen XL, Ai HS. HLA-mismatched stem-cell microtransplantation as postremission therapy for acute myeloid leukemia: long-term follow-up. *J Clin Oncol.* 2012 Nov 20;30(33):4084-90. doi: 10.1200/JCO.2012.42.0281. Epub 2012 Oct 8.

[figure not shown]

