6.3.2 Postremission treatment

Subjects who achieve a CR will receive 2 further courses of cytarabine postremission chemotherapy (consolidation) at 1.0 g/m^2 for 6 dosages followed by HLA-mismatched DLI after the second consolidation. Cytarabine will be given twice daily at 12 hour intervals on days 1, 3, and 5; HLA-mismatched DLI will be administered the day following the completion of the second consolidation (day 7) at a dose of $1 \times 10^8 \text{ CD3+ cells}$, although as above, a 24-96 hour interval between completion of chemotherapy and infusion of cells will be allowed for logistical reasons without being considered a protocol violation.

No cells will be given after the first consolidation, as chemotherapy given with the second consolidation will likely kill any cells infused after the first consolidation (i.e. infusion of cells after the first consolidation would be costly and low-yield) (Note that while this argument could also be applied to cells infused after induction, Guo et al. showed an improvement in the CR rate from 40% to 80% with the use of cells with induction, which is why we plan to use cells after induction in this trial).

The timing of consolidation typically takes place after count recovery, around 6-12 weeks after induction, following standard protocols and timing for cytarabine consolidation.

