6.4.6 Cytokine Release Syndrome

We will measure cytokine release with DLI based on peripheral blood analysis. Blood will be taken on the day of cell infusion for both induction and consolidation 2, to be drawn before infusion and 2 days after infusion for both induction and consolidation 2 to evaluate for cytokine release syndrome with DLI. For subjects who do not receive their DLI during induction but rather following consolidation #1 and consolidation #2, blood will be drawn before infusion and 2 days after infusion to measure cytokine release. We will use about 4-8 teaspoons of blood drawn from a vein by a needle-stick or through a central line each time you have these blood tests.

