11.0 STUDY DESIGN AND ANALYSIS

11.1 Primary Objectives:

10.1.1 Safety: Evaluate the safety of HLA-haploidentical DLI combined with conventional induction and consolidation chemotherapy in terms of unacceptable toxicity as defined in section 7.0.

A maximum of 30 subjects will be consented for a maximum of 21 evaluable subjects accrued to this protocol over a period of 2 years. Safety will be evaluated by the number of subjects with unacceptable toxicity as defined by any of the following:

- i. Grade III or IV aGVHD of the gut or liver or Grade IV aGVHD of the skin lasting > 7 days;
- ii. Grade IV CTCAE toxicity attributable to DLI (e.g. infusion reaction, as opposed to Grade IV CTCAE toxicity from chemotherapy) and lasting >7 days
- iii. Treatment-related mortality (TRM), keeping in mind that anticipated mortality from standard induction chemotherapy in the elderly ranges from 11% for subjects 55-65 years-old with ECOG 0 to 50% for subjects older than 75 years with ECOG 2 [1].

Simon's optimal two stage design will be applied. These rules permit the study to be closed early if there is evidence that the true unacceptable toxicity rate is ≥ 0.40 . The stopping rules in the table below will also allow us to test the null hypothesis that the true toxicity rate is ≥ 0.40 against the alternative hypothesis that the true toxicity rate is ≤ 0.20 . The Type I and II error rates for this design are 0.15 and 0.2, respectively. Given that the true toxicity rate is 0.40 (0.20), the probability of stopping the trial at Stage 1 to accept the null hypothesis is 0.7 (0.16). The significance level of this design is 0.15 and the power is 0.80.

| Stage | Total Accrual | Close study/therapy if number of subjects with unacceptable toxicity is \geq |
|-------|---------------|--|
| 1 | 11 | 4 (45%) |
| 2 | 21 | 7 (33%) |

Rates of unacceptable toxicity will be calculated and monitored with the stopping rules in the table above. Toxicity in the other categories will be informally monitored and tabulated by Type and Grade, but they will not be used to determine tolerability of the procedure.

Chemo with Adoptive Haplo DLI

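### Does allowing induction without cells mean that CR, response and count recovery must be split by cells with the first induction?

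*Combined protocol and SAP*

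**What the plan says.** The default is cells after IND1 and after the second consolidation (CON2). Section 6.3.1 adds a planned exception for cases where cells cannot be arranged in time: "patients would just receive standard induction chemotherapy and cells would be administered after CON1 in addition to CON2". It gives no expected frequency.

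Patients not in CR after IND1 are re-induced, and cells are again the default: "IND2 should include 7+3+DLI as per IND1, but if cells are not available as per 6.2.3, chemotherapy alone can be given". Section 6.3.2 limits consolidation to responders: "Subjects who achieve a CR will receive 2 further courses of cytarabine postremission chemotherapy". It justifies cells at induction by a cited study that "showed an improvement in the CR rate from 40% to 80% with the use of cells with induction". It also states that "No cells will be given after the first consolidation", without mentioning the exception in 6.3.1. Section 6.4.6 does carry the exception through, with blood draws "For subjects who do not receive their DLI during induction but rather following consolidation #1 and consolidation #2".

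On analysis, section 11.1 sets the numbers: "A maximum of 30 subjects will be consented for a maximum of 21 evaluable subjects". Sections 11.1.2 and 11.2.3 plan single CR and response rates with one-sided intervals (90% and 85%). Section 11.2.5 plans descriptive statistics for count recovery. The eight subgroup factors in 11.3 do not include cells with IND1, and *evaluable* is not defined anywhere.

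**The concern.** The protocol expects cells at induction to change CR, yet some patients may reach their CR assessment without having received any. One pooled rate does not show how many. A reader who sets it beside the 80% cited in sections 3.7 and 6.3.2 could take a diluted figure for a disappointing one, or credit the cells with remissions that chemotherapy alone produced.

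The undefined denominator adds a second worry. On the route without cells, the first infusion comes only after CR. If *evaluable* were read as having received an infusion, patients who fail chemotherapy-only induction would leave the denominator while those who respond would stay. CR would then rise by selection alone.

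**Working it through.** **The plan's own figures.** Neither a descriptive split nor a definition of *evaluable* that keeps N = 21 touches them.

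- Efficacy test, 0.20 against 0.45, N = 21, one-sided 0.05: power = Φ[(0.25·√21 − 1.645·√(0.20·0.80)) / √(0.45·0.55)] = Φ[(1.146 − 0.658)/0.497] = 0.837, against the stated 84% or so. The exact binomial rule (at least 8 of 21) has alpha 0.043 and power 0.803.
- Safety design, stopping at 4 of 11 or 7 of 21: early stopping 0.704 at a true rate of 0.40 and 0.161 at 0.20, type I error 0.150, power 0.801. These agree with the stated 0.7, 0.16, 0.15 and 0.80.

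**How far the mix moves the pooled CR.** Let f be the share induced without cells. The documents do not give it, so 0.1, 0.3 and 0.5 are assumed (about 2, 6 and 10 of 21 patients). CR with cells is 80% and without cells c = 42.8% (section 3.7, which used a different chemotherapy backbone). The range for c is 30% to 65% (section 3.1). All-treated CR = 0.80(1 − f) + c·f.

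| f | c = 0.428 | c = 0.30 | c = 0.65 |
|---|---|---|---|
| 0.1 | 0.763 | 0.750 | 0.785 |
| 0.3 | 0.688 | 0.650 | 0.755 |
| 0.5 | 0.614 | 0.550 | 0.725 |

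Each entry is the correct CR for a policy of giving cells at induction when feasible. None is a biased estimate of that quantity.

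**What a split could show.** Take f = 0.3, with 12/15 in CR with cells and 3/6 without, so 15/21 overall. The exact one-sided 90% lower bounds are 0.61, 0.20 and 0.55. At the 85% level they are 0.64, 0.24 and 0.58. The smaller group supports no comparison, and patients are not randomised to the two routes.

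**Selection if *evaluable* meant infused.** Suppose cells have no effect, no CR comes from re-induction (IND2), and a share q of chemotherapy-only failures receive cells at IND2. The infused set is 1 − f(1 − c)(1 − q) of all patients and contains every CR, so infused-only CR = c / [1 − f(1 − c)(1 − q)]. With c = 0.428:

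| f | q = 0 | q = 0.5 | q = 1 |
|---|---|---|---|
| 0.1 | 0.454 | 0.441 | 0.428 |
| 0.3 | 0.517 | 0.468 | 0.428 |
| 0.5 | 0.599 | 0.499 | 0.428 |

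The column q = 0 is the extreme. Section 6.3.1 makes cells the default at IND2, which moves q towards 1, where the inflation vanishes.

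**Is the infused reading likely?** Section 7.0 starts OS and EFS at the start of therapy, not at infusion. Its toxicity definition sets treatment-related mortality against deaths expected from standard induction chemotherapy. Both point to a set that begins with treatment. The gap between 30 and 21 is a difference of two maxima. It may include patients who consent but are never treated, so it is not evidence that treated patients will be dropped.

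**Which course count recovery refers to.** Section 6.4.2 schedules daily counts during induction and two-weekly counts after consolidation, and Appendix I has a count-recovery column for IND1 or IND2. Induction is the natural reading, although a footnote there extends the recovery period to consolidation.

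**Cells after the first consolidation.** Section 6.3.1 is worded as an exception for named circumstances, 6.3.2 as the general rule, and 6.4.6 follows the exception. What is missing is a cross-reference.

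**The case for a change.** The strongest case for a change is that it costs one table and a few sentences, and that fixing the denominator and the split before results are seen removes any later choice. The exposure is one the protocol itself regards as decisive for CR, and section 3.7 also cites faster neutrophil recovery (11 against 16 days) and platelet recovery (14.5 against 20 days) with cells. The nearest planned subgroup, post-infusion chimerism, is itself an outcome and cannot stand in for it.

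The infused reading also has some footing. Toxicity follow-up runs to 8 weeks after the last infusion, section 11.1.2 describes 1-year DFS as following the cell transfer, and Appendix I drops the listed assessments for patients who do not complete therapy.

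Some of this stands. The term *evaluable* is undefined, and it governs the safety and DFS sets as well as CR. If only 17, 15 or 12 patients counted for DFS (assumed numbers), exact power would be 71%, 55% or 47%. But that question arises because section 7.0 starts DFS at CR. It would be the same if every patient had cells with IND1, so the route without cells does not create it. The proposed split also leaves part of its own question open: grouping by IND1 places patients who receive cells at IND2 with those who had none, while grouping by any cells before assessment selects on non-response.

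**Conclusion.** No change to the plan follows. The description of the text is accurate, but the pooled CR, response and count-recovery figures are valid summaries of the strategy as written. The suggested split would describe groups of perhaps 15 and 6 patients and could not show what the cells do. The plan already has the cell content of infusions monitored (6.2.3) and blood drawn around them (6.4.6). The number of patients with cells at IND1 and at IND2, and a table by IND1, can therefore be reported without an amendment.

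The inflation of CR is conditional. At f = 0.3 and c = 42.8%, with no effect of cells and no CR from IND2, it runs from nothing to about 9 percentage points (51.7% against 42.8%). It arises only under a reading of *evaluable* that no section states and that sits poorly with endpoints timed from the start of therapy. The sensible reading is one set for safety and response that keeps treated patients who fail or die during chemotherapy-only induction.

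The missing cross-reference between 6.3.1 and 6.3.2 is clerical. The two passages should be reconciled when the text is next edited. The conclusion would weaken if most patients were induced without cells, but the protocol presents that route as an occasional exception.

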6.3.2 Postremission treatment

Subjects who achieve a CR will receive 2 further courses of cytarabine postremission chemotherapy (consolidation) at 1.0 g/m^2 for 6 dosages followed by HLA-mismatched DLI after the second consolidation. Cytarabine will be given twice daily at 12 hour intervals on days 1, 3, and 5; HLA-mismatched DLI will be administered the day following the completion of the second consolidation (day 7) at a dose of $1 \times 10^8 \text{ CD3+ cells}$, although as above, a 24-96 hour interval between completion of chemotherapy and infusion of cells will be allowed for logistical reasons without being considered a protocol violation.

No cells will be given after the first consolidation, as chemotherapy given with the second consolidation will likely kill any cells infused after the first consolidation (i.e. infusion of cells after the first consolidation would be costly and low-yield) (Note that while this argument could also be applied to cells infused after induction, Guo et al. showed an improvement in the CR rate from 40% to 80% with the use of cells with induction, which is why we plan to use cells after induction in this trial).

The timing of consolidation typically takes place after count recovery, around 6-12 weeks after induction, following standard protocols and timing for cytarabine consolidation.

6.3.3 Dose Adjustments

Patients with Hepatic Impairment Dosing: Dosage will be modified depending on clinical response and degree of hepatic impairment, but no quantitative recommendations are available.

Subjects with Renal Impairment Dosing:

Our program follows the following guidelines: Estimate a creatinine clearance using the formula for the estimated CrCl in ml/min:

$(140 - \text{age})/\text{serum Cr} \times (\text{ideal body wt}/72)$.

In addition, for females this value is multiplied by .85

For subjects with a CrCl > 60 ml/min: No dosage adjustment.

CrCl <= 60 ml/min: There is an increased risk of cerebellar and cerebral toxicity with high dose regimens. The recommended dosage adjustment will be as follows: For a serum creatinine of 1.5—1.9 mg/dl or increase of serum creatinine from baseline of 0.5—1.2 mg/dl during treatment, the dose of cytarabine will remain 100 mg/m² during induction and be reduced to 500 mg/m² during postremission therapy. For a serum creatinine \geq 2 mg/dl or if the change in baseline serum creatinine was > 1.2 mg/dl, we will reduce the dose of cytarabine to 50 mg/m² during induction and to 250 mg/m² during postremission therapy.

6.3.4 DLI

Allogeneic DLI will be collected from the donor as described in section 6.2.2. The allogeneic DLI will be infused as per current practice.

Subjects will be given premedications including Benadryl 25 mg IV, and Acetaminophen 650 mg po prior to infusion. Hydrocortisone is used at the physician's discretion.

If needed, modifications to the infusion rate may be made as per standard practice.

6.3.5 Supportive Care

GVHD prophylaxis: GVHD prophylaxis will not be administered.

Growth factor use: A growth factor of choice may be initiated at the treating physician's discretion.

Antibiotic prophylaxis (may be altered to follow the treating physicians standard practice without affecting overall study):

- a. Voriconazole 200 mg PO BID or Posaconazole 200 mg PO TID beginning at day 9 (or Day 7 for subjects receiving 5+2 regimen) until CD4+ >200/uL or 1 year following therapy, whichever occurs first. Alternatives may be substituted at the physician's discretion.

Chemo with Adoptive Haplo DLI

- b. Acyclovir 400 mg PO BID beginning day 9 (or Day 7 for subjects receiving 5+2 regimen) until ANC > 1000/uL or day +30 if a donor or recipient is only HSV seropositive; acyclovir 800mg PO BID will continue from day +30 through 1 year or until CD4 count is >200/uL if a donor or recipient is VZV seropositive.
- c. Ciprofloxacin 500mg po BID should be initiated beginning on day 9 (or Day 7 for subjects receiving 5+2 regimen) and continue until CD4 count >200/uL or 1 year following therapy if tolerated orally. Alternative prophylactic antibiotics may be used at the physician's discretion.
- d. CMV monitoring will occur at baseline. The treating physicians may use their own test of choice for this surveillance, though a PCR based assay is recommended. A positive test necessitates initiating therapy per local standards (low positive typically requires a repeat confirmation and a high positive immediate initiation of anti-CMV therapy with ganciclovir or foscarnet).

Blood products: All blood products (except DLI) will be irradiated following local standards to prevent possible GVHD. Hematocrit should be maintained at $\geq 25\%$, and platelets at $> 10,000/\text{mm}^3$ (subject to treating physician discretion). All blood products should be filtered prior to infusion

Other care: Agents designed to minimize other side effects of transplantation such as decreasing mucositis are allowed at the physician's discretion.

6.4 Subject Evaluation

6.4.1 Clinical Evaluation

Subjects will be evaluated daily during induction and recovery from therapy while admitted to the hospital. Evaluation will include history and physical exam and toxicity monitoring, including acute GVHD monitoring. They will return for post-remission therapy and typically be re-admitted to our service for further treatment. In selected cases, subjects may remain outpatient with very close care and follow up per the treating team's discretion. Upon completion of therapy, they will be seen at least every other week until 8 weeks, after which they will be seen at least every 3 months for 2 years.

6.4.2 Laboratory and other testing

(Correlative Studies for 00043247 v. 15.06.19 Lab Manual)

Evaluation for supportive care during therapy/recovery and after therapy will be as follows (Recommended but may change based on clinical status per treating physician):

- (a) CBC will be obtained daily during induction until transfusions of platelets and red blood cells are not regularly required, then as clinically indicated. When the white count reaches greater than

Chemo with Adoptive Haplo DLI

500/uL, then add differential and follow to document when ANC > 1,500/uL. After consolidation, CBC and differential will be checked every 2 weeks or as clinically indicated.

- (b) Serum chemistries and liver functioning tests at least weekly and as clinically indicated while during therapy/recovery; chemistries and liver function tests will also be checked at 8 weeks and then every 3 months for 2 years.
- (c) Serum quantitative beta-HCG will be checked one week prior to induction in females.
- (d) Biopsies of organs suspected to be involved with GVHD as clinically indicated (e.g., skin, liver, GI tract).
- (e) Chest X-ray as clinically indicated.
- (f) Bone marrow biopsy at Day 14 (per investigator discretion) as well as after count recovery (mandatory)
- (g) HLA Antibodies at count recovery and 8 weeks after CON2.
- (h) For patients who relapse or have refractory disease going off study, collect the following labs: peripheral blood for minimal residual disease testing, NK lysis assay, microchimerism, TCR sequencing, PD1/PDL1/PDL2 expression.

6.4.3 Detection of donor chimerism and microchimerism:

Hematopoietic donor chimerism will be assessed in all subjects with the use of standard cytogenetic and semiquantitative PCR-based analysis of short tandem repeats with 1% sensitivity.

Microchimerism will be analyzed using real time PCR (qPCR) at a sensitivity of 1/100,000.

These assays will be performed at count recovery prior to each new cycle of therapy, at 8 weeks after the last round of consolidation, and if still positive, every 3 months after completing therapy for up to two years. Additionally, in the case of mother-child pairs or sibling pairs that are mismatched in NIMA, this will be conducted before first infusion to assess for persistent maternal-fetal microchimerism.

6.4.4 Evaluation of immune function

We will evaluate immune function based peripheral blood and bone marrow analysis using the following assays:

1. Cytokines will be measured, particularly levels of IL1, IL1beta, CRP, IL2, IL6, IL8, IL15, IL21, IFN-gamma, TNF-alpha, TGF-beta
2. Lymphocyte subsets will be analyzed using flow cytometric lymphocyte immunotyping with fluorochrome conjugated monoclonal antibodies to CD3, CD4, CD8, CD11c, CD16, CD19, CD25, CD28, CD45RA/RO, CD56, CD57, CD62L, CD107, CD123, TCR gamma-delta, FOXP3, HLA, and KIR
3. Quantification of recent thymic immigrants will be determined by the presence of TCR rearrangement excision circles (TREC), retrospectively performed by real-time quantitative-PCR of DNA collected from an isolated fraction of CD31 T cells and next

generation sequencing to analyze diversity in the TCR repertoires produced by the rearrangements of the variable region genes.

4. NK activity will be assessed by FACS (CD56+CD107+).
These assays will be done at count recovery prior to each new cycle of therapy, at 8 weeks after the last round of consolidation, and every 3 months after completing therapy for up to two years.
Additional blood will not be drawn for this testing.

